10.3.4 Additional Protocol-Specific Expedited Adverse Event Reporting Exclusions

For this protocol only, the AEs/grades listed below do not require expedited reporting via CTEP-AERS. However, they still must be reported through the routine reporting mechanism (Section 10.4):

CTCAE SOC	Adverse Event	Grade	≥24h Hospitalization ^a
Blood and lymphatic disorders	Bone marrow hypocellular	4	Regardless
Cardiac Disorders	Atrial fibrillation	2	Regardless
Cardiac Disorders	Atrial flutter	2	Regardless
Ear and labyrinth disorders	Vertigo	2	Regardless
Gastrointestinal disorders	Belching	2	Regardless
Gastrointestinal disorders	Bloating	2	Regardless
Gastrointestinal disorders	Constipation	3	Regardless
Gastrointestinal disorders	Dental caries	3	Regardless
Gastrointestinal disorders	Dry mouth	2	Regardless
Gastrointestinal disorders	Dyspepsia	3	Regardless
Gastrointestinal disorders	Gastroesophageal reflux disease	2	Regardless
Gastrointestinal disorders	Gingival pain	2	Regardless
Gastrointestinal disorders	Hemorrhoids	2	Regardless
Gastrointestinal disorders	Lip pain	3	Regardless

CTCAE SOC	Adverse Event	Grade	≥24h Hospitalization^a
Gastrointestinal disorders	Toothache	3	Regardless
General disorders and administration site conditions	Infusion site extravasation	2	Regardless
General disorders and administration site conditions	Malaise	3	Regardless
General disorders and administration site conditions	Pain	2	No
Injury, poisoning and procedural complications	Fracture	2	Regardless
Investigations	Activated partial thromboplastin time prolonged	3	No
Investigations	Blood lactate dehydrogenase increased	1	Regardless
Investigations	INR increased	3	No
Metabolism and nutrition disorders	Glucose intolerance	3	Regardless
Metabolism and nutrition disorders	Hypercalcemia	2	No
Metabolism and nutrition disorders	Hyperglycemia	3	No
Metabolism and nutrition disorders	Hyperkalemia	2	No
Metabolism and nutrition disorders	Hypernatremia	2	No
Metabolism and nutrition disorders	Hyperphosphatemia	3	No
Metabolism and nutrition disorders	Hyperuricemia	3	No
Metabolism and nutrition disorders	Hypalbuminemia	3	No
Metabolism and nutrition disorders	Hypocalcemia	2	No
Metabolism and nutrition disorders	Hypoglycemia	2	No
Metabolism and nutrition disorders	Hypokalemia	3	No
Metabolism and nutrition disorders	Hypomagnesemia	2	No

CTCAE SOC	Adverse Event	Grade	≥24h Hospitalization ^a
Metabolism and nutrition disorders	Hyponatremia	3	No
Metabolism and nutrition disorders	Hypophosphatemia	3	No
Metabolism and nutrition disorders	Obesity	4	Regardless
Metabolism and nutrition disorders	Tumor lysis syndrome	3	No
Psychiatric disorders	Agitation	3	Regardless
Psychiatric disorders	Anxiety	3	Regardless
Psychiatric disorders	Delirium	3	Regardless
Psychiatric disorders	Depression	3	Regardless
Psychiatric disorders	Insomnia	3	Regardless
Renal and urinary disorders	Chronic kidney disease	4	Regardless
Renal and urinary disorders	Dysuria	1	Regardless
Renal and urinary disorders	Urinary frequency	2	Regardless
Respiratory, thoracic, and mediastinal disorders	Hiccups	3	No
Respiratory, thoracic, and mediastinal disorders	Nasal congestion	3	Regardless
Respiratory, thoracic, and mediastinal disorders	Sneezing	2	Regardless
Respiratory, thoracic, and mediastinal disorders	Sore throat	3	No
Respiratory, thoracic, and mediastinal disorders	Sleep apnea	3	Regardless
Skin and subcutaneous tissue disorders	Dry skin	3	Regardless
Skin and subcutaneous tissue disorders	Eczema	3	No
Vascular disorders	Hypertension	3	No
Vascular disorders	Thromboembolic event	2	No

^a Indicates that an adverse event required hospitalization for ≥24 hours or prolongation of hospitalization by ≥24 hours of a patient.

10.4 Routine Adverse Event Reporting

All Adverse Events **must** be reported in routine study data submissions. **AEs reported**

expeditiously through CTEP-AERS must also be reported in routine study data submissions.

Adverse event data collection and reporting, which are required as part of every clinical trial, are done to ensure the safety of patients enrolled in the studies as well as those who will enroll in future studies using similar agents. AEs are reported in a routine manner at scheduled times during the trial using Medidata Rave. For this trial the Adverse Event CRF is used for routine AE reporting in Rave.

10.5 Pregnancy

Although not an adverse event in and of itself, pregnancy as well as its outcome must be documented via **CTEP-AERS**. In addition, the ***Pregnancy Information Form*** included within the NCI Guidelines for Adverse Event Reporting Requirements must be completed and submitted to CTEP. Any pregnancy occurring in a patient or patient's partner from the time of consent to 90 days after the last dose of study drug must be reported and then followed for outcome. Newborn infants should be followed until 30 days old. Please see the "NCI Guidelines for Investigators: Adverse Event Reporting Requirements for DCTD (CTEP and CIP) and DCP INDs and IDEs" (at http://ctep.cancer.gov/protocolDevelopment/adverse_effects.htm) for more details on how to report pregnancy and its outcome to CTEP.

10.6 Secondary Malignancy

A *secondary malignancy* is a cancer caused by treatment for a previous malignancy (e.g., treatment with investigational agent/intervention, radiation or chemotherapy). A secondary malignancy is not considered a metastasis of the initial neoplasm.

CTEP requires all secondary malignancies that occur following treatment with an agent under an NCI IND/IDE be reported expeditiously via CTEP-AERS. Three options are available to describe the event:

- Leukemia secondary to oncology chemotherapy (e.g., acute myelocytic leukemia [AML])
- Myelodysplastic syndrome (MDS)
- Treatment-related secondary malignancy

Any malignancy possibly related to cancer treatment (including AML/MDS) should also be reported via the routine reporting mechanisms outlined in each protocol.

10.7 Second Malignancy

A second malignancy is one unrelated to the treatment of a prior malignancy (and is **NOT** a metastasis from the initial malignancy). Second malignancies require **ONLY** routine AE reporting unless otherwise specified.

11. STUDY CALENDAR

Baseline evaluations are to be conducted within 14 days prior to start of protocol therapy. Scans and x-rays must be done ≤4 weeks prior to the start of therapy.

In the event that the patient’s condition is deteriorating, laboratory evaluations should be repeated within 48 hours prior to initiation of the next cycle of therapy.

	Pre-Study	Wk 1 Cyc 1 Day 1	Cyc 1 Day 8	Wk 3	Wk 4	Wk 5 Cyc 2 Day 1	Wk 6	Wk 7	Wk 8	Wk 9 Cyc 3 Day 1	Wk 10	Wk 11	Wk 12
Pinometostat		A	A	A	A	A	A	A	A	A	A	A	A
Azacitidine		B				B				B			
Informed consent	X												
Demographics	X												
Medical history	X												
Hepatitis B and C testing	X												
Concurrent meds	X	X-----X											
Physical exam	X	X		X		X				X			
Urine Pregnancy Test	X												
Vital signs	X	X		X		X				X			
Height	X												
Weight	X	X		X		X				X			
Performance status	X	X											
CBC w/diff, plts	X	X	X	X	X	X				X			
Serum chemistry ^a	X	X	X	X	X	X				X			
PT / PTT	X	X	X	X	X	X				X			
Uric Acid	X	X											
Serum PK assessments ^b		X											
Serum 5-aza-2'-deoxycytidine genomic incorporation ^c		X	X										
EKG (as indicated)	X	X	X	X	X								
Adverse event evaluation		X-----X											
Nail clippings collection	X												

Bone Marrow Biopsy and Aspirate (with morphology, flow cytometry, cytogenetics, FISH)	X					X†								
Marrow aspirate myeloid genomic panel	X													
Marrow aspirate for banking samples	X					X†								
Marrow aspirate for qPCR for HOXA9 & Meis1 and H3K79 ELISA	X					X†								
Marrow aspirate for 5-aza-2'-deoxycytidine Genomic Incorporation and DNA demethylation ^c	X					X†								

A: *Pinometostat*: Dose as assigned
 B: *Azacitidine*: Standard dosing of 75mg/m² given over 7 of the first 10 days of the cycle
 a: Albumin, alkaline phosphatase, total bilirubin, bicarbonate, BUN, calcium, chloride, creatinine, glucose, phosphorus, potassium, total protein, SGOT [AST], SGPT [ALT], sodium, magnesium.
 b: PK assessments should be done prior to treatment and at 15, 30, and 60 min after azacitidine is started in cycle 1
 c: Serum and marrow 5-aza-2'-deoxycytidine genomic incorporation and DNA demethylation samples must be collected in green-top vacutainer containing THU
 †: Bone marrow tests should be performed at the end of cycle 1, end of cycle 3, and end of cycle 6, prior to the start of the next cycle of azacitidine. These can be performed on the first day of the following cycle, prior to the start of azacitidine therapy.

	Wk 13 Cyc 4 Day 1	Wk 14	Wk 15	Wk 16	Wk 17 Cyc 5 Day 1	Wk 18	Wk 19	Wk 20	Wk 21 Cyc 6 Day 1	Wk 22	Wk 23	Wk 24	Off Study ^c	1- mo f/u
Pinometostat	A	A	A	A	A	A	A	A	A	A	A	A	#	
Azacitidine	B				B				B					
Informed consent														
Demographics														
Medical history														
Concurrent meds	X-----X													
Physical exam	X				X				X				X	X
Vital signs	X				X				X				X	X
Height	X													
Weight	X				X				X				X	X

Performance status															
CBC w/diff, plts	X				X				X				X	X	
Serum chemistry ^a	X				X				X				X	X	
PT/PTT	X				X				X				X	X	
EKG (as indicated)															
Adverse event evaluation	X-----X														
Bone Marrow Biopsy and Aspirate (with morphology, flow cytometry, cytogenetics, FISH)	X [‡]												X [*]		
Marrow aspirate for banking samples	X [‡]												X [*]		
Marrow aspirate for qPCR for HOXA9 & Meis1 and H3K79 ELISA	X [‡]												X [*]		
Marrow aspirate for 5-aza-2'-deoxycytidine Genomic Incorporation and DNA demethylation ^c	X [‡]												X [*]		

A: Pinometostat: Dose as assigned
 B: Azacitidine: Standard dosing of 75 mg/m2 given over 7 of the first 10 days of the cycle
 a: Albumin, alkaline phosphatase, total bilirubin, bicarbonate, BUN, calcium, chloride, creatinine, glucose, phosphorus, potassium, total protein, SGOT [AST], SGPT [ALT], sodium, magnesium.
 c: Serum and marrow 5-aza-2'-deoxycytidine genomic incorporation and DNA demethylation samples must be collected in green-top vacutainer containing THU
 ‡: Bone marrow tests should be performed at the end of cycle 1, end of cycle 3, and end of cycle 6, prior to the start of the next cycle of azacitidine. These tests can be performed on the first day of the following cycle, prior to the start of azacitidine therapy.
 *: Bone marrow tests should be done at the end of cycle 6. If a patient receives fewer than 6 cycles or more than 6 cycles, bone marrow tests should be done at the time of therapy cessation as long as at least one month has elapsed since the prior bone marrow test.
 #: For patients who continue on pinometostat beyond 6 months, they should follow the same evaluation schedule as outlined for cycle 2.

12. MEASUREMENT OF EFFECT

Although the clinical benefit of these drugs has not yet been established, the intent of offering this treatment is to provide a possible therapeutic benefit, and thus the patient will be carefully monitored for tumor response and symptom relief in addition to safety and tolerability. Patients with measurable disease will be assessed by standard criteria. For the purposes of this study, patients should be re-evaluated at the end of cycle 1, end of cycle 3, and end of cycle 6.

12.1 Antitumor Effect

For the purposes of this study, patients should be re-evaluated for response at the end of cycle 1, end of cycle 3, and end of cycle 6.

Response and progression will be evaluated in this study using the 2017 European Leukemia Net Guidelines¹⁹.

12.1.1 Definitions

Evaluable for toxicity. All patients will be evaluable for toxicity from the time of their first treatment with pinometostat.

Evaluable for objective response. Only those patients who have measurable disease present at baseline, have received at least one cycle of therapy, and have had their disease re-evaluated will be considered evaluable for response. These patients will have their response classified according to the definitions stated below. (Note: Patients who exhibit objective disease progression prior to the end of cycle 1 will also be considered evaluable.)

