9.5.2 Evaluation of Response

All patients included in the study must be assessed for response to treatment, even if there are major protocol treatment deviations or if they are ineligible. Each patient will be assigned one of the following categories: 1) complete response, 2) partial response, 3) stable disease, 4) morphologic leukemia-free state, 5) early death from malignant disease, 6) early death from toxicity, 7) early death because of other cause, 8) progressive disease, or 9) unknown (not assessable, insufficient data). [Note: By arbitrary convention, category 9 usually designates the “unknown” status of any type of data in a clinical

database.]

All of the patients who met the eligibility criteria (with the possible exception of those who received no study medication) should be included in the main analysis of the response rate. Patients in response categories 5-9 should be considered to have a treatment failure (disease progression). Thus, an incorrect treatment schedule or drug administration does not result in exclusion from the analysis of the response rate. Precise definitions for categories 4-9 will be protocol specific.

All conclusions should be based on all eligible patients. Subanalyses may then be performed on the basis of a subset of patients, excluding those for whom major protocol deviations have been identified (*e.g.*, early death due to other reasons, early discontinuation of treatment, major protocol violations, etc.). However, these subanalyses may not serve as the basis for drawing conclusions concerning treatment efficacy, and the reasons for excluding patients from the analysis should be clearly reported. The 95% confidence intervals should also be provided.

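### Does the narrower evaluable set in 12.1.1, or the absence of CRi from the category list in 9.5.2, leave the phase II response analysis undefined?

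*Combined protocol and SAP*

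**What the plan says.** Section 9.5.2 (Evaluation of Response) states that "All patients included in the study must be assessed for response to treatment", including patients who are ineligible or had major treatment deviations. Each patient receives one of nine categories. The main analysis of response rate takes in all patients who met the eligibility criteria, "with the possible exception of those who received no study medication". Categories 5 to 9 (three kinds of early death, progression, unknown) are treatment failures. It adds that "All conclusions should be based on all eligible patients". Analyses that leave out patients with, for example, early discontinuation are allowed, but "these subanalyses may not serve as the basis for drawing conclusions concerning treatment efficacy".

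Section 12.1.1 (Definitions) sets up a narrower group for objective response: only patients with measurable disease at baseline who "have received at least one cycle of therapy, and have had their disease re-evaluated will be considered evaluable for response". A note extends it: "Patients who exhibit objective disease progression prior to the end of cycle 1 will also be considered evaluable".

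Section 9.4 plans a report on all patients, all eligible patients and all evaluable patients.

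The non-failure categories in 9.5.2 are "1) complete response, 2) partial response, 3) stable disease, 4) morphologic leukemia-free state". CRi is not listed. It is part of the response definition in 9.1, 9.4 and 12.1.4.3, and has its own definition in 12.1.4.1.

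**The concern.** Read alone, 12.1.1 is a denominator rule. A patient who dies early without documented progression, withdraws in cycle 1 or is never re-evaluated is a failure under 9.5.2 but outside the evaluable set under 12.1.1. Section 12.1.1 does not call itself supportive, 9.4 does not rank its three populations, and 9.1 gives the 19 and 36 without naming a set. If the 19 and 36 were filled with evaluable patients only, likely non-responders would be replaced and the false-positive probability would rise.

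The CRi omission raises a second worry. Assignment to one of the nine categories is mandatory, and the primary endpoint includes a response that has no category. If CRi patients were coded outside the responses, power would fall. If they were coded as CR or MLFS, the split between response types would blur.

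**Working it through.** **Inputs.** All from 9.1: unpromising rate 20%, promising rate 40%, both error limits 0.10; 19 patients in stage 1, continue with at least 4 responders; 17 more; positive with at least 11 of 36.

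**Step 1: the plan's own figures.** With X1 ~ Bin(19, p) and X2 ~ Bin(17, p),

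P(positive) = Σ (x = 4 to 19) P(X1 = x) · P(X2 ≥ 11 − x).

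At p = 0.20 the terms for x = 4 to 11 are 0.0082 + 0.0173 + 0.0231 + 0.0200 + 0.0115 + 0.0045 + 0.0012 + 0.0003 = 0.0861; later terms are negligible. The probability of a negative result is 1 − 0.0861 = 0.914, against 0.90 stated. At p = 0.40 the sum is 0.902, against at least 0.90 stated. The design is reproduced.

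**Step 2: which patients are the 36?**

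| Patient | 9.5.2 | 12.1.1 |
|---|---|---|
| Re-evaluated after at least one cycle | category by response | evaluable |
| Objective progression before end of cycle 1 | category 8, failure | evaluable |
| Early death, no documented progression | category 5, 6 or 7, failure | not evaluable |
| Never re-evaluated | category 9, failure | not evaluable |

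The sections differ only in the last two rows. Only 9.5.2 says which set carries the main analysis and the conclusions. They can also be read together: re-evaluated patients are classified by the ELN definitions, and the rest receive a 9.5.2 category. Section 12.1.1 then supplies the third population in the 9.4 report.

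**Step 3: effect without replacement.** The rule is a count, so a non-evaluable patient adds no responder whichever denominator is printed. Taking 11 responders and assuming 4 non-evaluable patients:

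- all eligible: 11/36 = 30.6% (exact 95% CI 16.3 to 48.1);
- evaluable only: 11/32 = 34.4% (18.6 to 53.2).

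The trial is positive either way.

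**Step 4: the hypothetical with replacement.** Suppose a share d of eligible patients is non-evaluable, all of them non-responders, the all-eligible rate is 20%, and accrual continues until 36 are evaluable. The rate among those counted is 0.20/(1 − d):

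| d (assumed) | rate counted | P(positive) |
|---|---|---|
| 5% | 21.1% | 0.115 |
| 10% | 22.2% | 0.153 |
| 15% | 23.5% | 0.203 |
| 20% | 25.0% | 0.268 |

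The 0.10 limit is passed at d of about 2.6%. This needs a replacement rule that phase II does not have; the only wording on replacement in 9.1 concerns DLT evaluability in phase Ib. The documents give no figure for d.

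**Step 5: where a CRi goes.** In 12.1.4.1, CRi requires marrow blasts under 5%, no circulating blasts, no Auer rods, no extramedullary disease, and incomplete count recovery. MLFS requires marrow blasts under 5%, no Auer rods and no extramedullary disease, without any count requirement. Every CRi therefore also satisfies the MLFS wording and fits category 4. It cannot be stable disease, because 12.1.4.1 defines that by the absence of CR, CRi, MLFS and PR. Coded as category 1 or 4, it leaves the overall response rate unchanged.

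**The case for a change.** The best case for a change is that the wording really is unreconciled. Section 12.1.1 does not cite 9.5.2, 9.1 cites neither, and the margin is thin if someone did replace patients: about one non-evaluable patient in 36 would take the false-positive probability past 0.10. Section 9.5.2 also leaves never-treated patients open, and 4.4 only says that their registration may be cancelled. Losing CRi would be costly too: if 10%, 20% or 30% of true responders (assumed shares) were CRi and not counted, power at a true 40% would be 0.792, 0.624 or 0.418.

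What stands is a missing cross-reference and a missing label. The inflation figures describe a rule the plan does not contain, and they also require the 20% to mean an all-eligible rate while only evaluable patients are counted. The power losses require a coding that contradicts 9.1, 9.4 and 12.1.4.3. Coding CRi as CR would blur the duration of CR in 12.1.5, and coding it as MLFS would mix those two groups. However, neither a CR-only nor an MLFS-only rate, nor a duration of CR, is an endpoint in 9.1 or 9.4. The blood counts that separate CR from CRi are on the study calendar, so the split can be recovered.

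**Conclusion.** No change to the plan is needed. The analysis set is fixed by 9.5.2: all eligible patients, with categories 5 to 9 as failures and subset analyses barred from supporting efficacy conclusions. The evaluable set in 12.1.1 is then the secondary population of the 9.4 report. On that reading the design keeps its error rates (0.086 at 20%, 0.902 at 40%), and the choice of denominator moves only a reported percentage, by 34.4 − 30.6 = 3.8 points in the example with 4 assumed non-evaluable patients. The absent CRi entry is a clerical slip in a list; the endpoint itself is defined with CRi in three places. An analyst following 9.1 and 9.5.2 would reach the same count and the same decision. The conclusion rests on 9.5.2 being followed as written, on no replacement of phase II patients, and on CRi being recorded under a response category.

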12.1.2 Disease Parameters

Measurable disease. For previously untreated patients, the presence of at least 20% blasts in the peripheral blood on a complete blood count differential or on a bone marrow aspirate differential, with cytogenetics or FISH studies showing a translocation or cytogenetics or FISH or a myeloid mutational panel showing partial tandem duplication of the 11q23 / MLL locus would qualify as measurable disease. For patients with relapsed / refractory disease, any abnormal disease burden as detected by morphology, flow cytometry, cytogenetics, or molecular testing which has a detectable 11q23 rearrangement or PTD would qualify as having measurable disease. Patients in either setting with a myeloid sarcoma or extramedullary involvement with detectable 11q23 rearrangement / PTD would also qualify as having measurable disease. Diagnosis should be confirmed with a bone marrow biopsy within 14 days prior to the start of therapy.

Measurable extramedullary lesions are defined as those that can be accurately measured in at least one dimension (longest diameter to be recorded) as ≥ 20 mm (≥ 2 cm) by chest x-ray or as ≥ 10 mm (≥ 1 cm) with CT scan, MRI, or calipers by clinical exam. All tumor measurements must be recorded in millimeters (or decimal fractions of centimeters).

Note: Tumor lesions that are situated in a previously irradiated area might or might not be considered measurable. *If the investigator thinks it appropriate to include them, the conditions under which such lesions should be considered must be defined in the protocol.*

Malignant lymph nodes. To be considered pathologically enlarged and measurable, a lymph node must be ≥ 15 mm (≥ 1.5 cm) in short axis when assessed by CT scan (CT scan slice thickness recommended to be no greater than 5 mm [0.5 cm]). At baseline and in follow-up, only the short axis will be measured and followed.

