- Response to combination therapy defined as CR, CRi, PR, or MLFS, with or without minimal residual disease (MRD), on bone marrow biopsy as defined by the 2017 European Leukemia Network guidelines will be assessed. Baseline bone marrow biopsy will be performed within 14 days prior to starting therapy, at the end of cycle 1 (day 28 +/- 2 days or time of count recovery), at the end of cycle 3 (+/- 2 days or at the time of count recovery after three cycles of azacitidine administration), at the end of cycle 6 (+/- 2 days or at the time of count recovery after six cycles of azacitidine administration), and / or at the time of therapy discontinuation +/- 3 days. Patients who have stable disease after 4 cycles of combination therapy or progressive disease at any time should be taken off the trial.

Phase II Primary Endpoint Analytic Plan:

- Response rate will be defined as the number of patients who achieve a CR, CRi, PR, or morphologic leukemia-free state (MLFS), with or without MRD, at any time point. Patients will be evaluated through the time of count recovery after 6 cycles of combination therapy.
- A Simon two-stage minimax design will be employed whereby a 20% response rate is considered not promising, a 40% response rate is considered promising, and the probabilities of a type I error (falsely accepting a non-promising therapy) and type II error (falsely rejecting a promising therapy) are set at 0.10 and 0.10, respectively. In the first stage of this design, 19 patients will be accrued. All patients will be followed for a minimum of 24 weeks. If at least 4 patients respond then an additional 17 patients will be accrued to the second stage. At the end of the trial, if 11 or more patients respond out of a total of 36 patients, then this combination will be considered worthy of further investigation. This design yields at least a 0.90 probability of a positive result if the true response rate is at least 40% and yields a 0.90 probability of a negative result if the true response rate is 20%.

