12.1.3 Methods for Evaluation of Measurable Disease

Hematopathology – The percentage of blasts found on the aspirate differential as read by the hematopathologist at the enrolling institution will be used to evaluate response.

Peripheral Blood CBC and Differential – The ANC, platelet count, and differential, including blast percentage from both automated and manual differentials, will be used. If both an automated and manual differential are performed, the latter will be used to evaluate the peripheral blast percentage.

FDG-PET - While FDG-PET response assessments need additional study, it is sometimes reasonable to incorporate the use of FDG-PET scanning to assess diagnosis and progression (particularly possible 'new' disease). This would only be applicable to patients with extramedullary disease. New lesions on the basis of FDG-PET imaging can be identified according to the following algorithm:

- a. Negative FDG-PET at baseline, with a positive FDG-PET at follow-up is a sign of PD based on a new lesion.
- b. No FDG-PET at baseline and a positive FDG-PET at follow-up: If the positive FDG-PET at follow-up corresponds to a new site of disease, this area should be biopsied to determine if it represents progression of disease. Such cases should be discussed with the medical monitor.
- c. FDG-PET may be used to upgrade a response to a CR for a patient with extramedullary disease, no bone marrow involvement, and no other means by which to evaluate their disease involvement (e.g. physical exam) in a manner similar to a biopsy in cases where a residual radiographic abnormality is thought to represent fibrosis or scarring. However, it must be acknowledged that such an approach may lead to false positive CR due to limitations of FDG-PET and biopsy resolution/sensitivity.

Note: A 'positive' FDG-PET scan lesion means one which is FDG avid with an uptake greater than twice that of the surrounding tissue on the attenuation corrected image.

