12.1.4 Response Criteria

12.1.4.1 Evaluation of Response as per 2017 ELN Guidelines¹⁹

Complete Remission (CR): Bone marrow blasts < 5%; no circulating blasts, no blasts with Auer rods, no extramedullary disease; ANC > 1000 per microliter, platelets > 100,000 per microliter

Complete Remission with Incomplete Count Recovery(CRi): Bone marrow blasts < 5%; no circulating blasts, no blasts with Auer rods, no extramedullary disease; ANC ≤ 1000 per microliter and / or platelets ≤ 100,000 per microliter

Morphologic Leukemia-Free State (MLFS): Bone marrow blasts < 5%; no blasts with Auer rods, no extramedullary disease; no hematologic recovery required

Partial Remission (PR): All hematologic criteria of CR; decrease in bone marrow blasts to 5-25%; decrease in pre-treatment bone marrow blasts by at least 50%

Progressive Disease (PD): Evidence for an increase in bone marrow blast percentage and/or increase of absolute blast counts in the blood:

- > 50% increase in marrow blasts over baseline (a minimum 15% point increase is required in cases with < 30% blasts at baseline; or persistent marrow blast percentage of >70% over at least 3 mo; without at least a 100% improvement in ANC to an absolute level ($>0.5 \times 10^9 /L$ [500/ μ L], and/or platelet count to $>50 \times 10^9 /L$ [50,000/ μ L] nontransfused); or
- > 50% increase in peripheral blasts (WBC x % blasts) to $>25 \times 10^9 /L$ ($>25,000/\mu$ L) (in the absence of differentiation syndrome); or
- New extramedullary disease

Stable Disease (SD): Absence of CR, CRi, MLFS, PR; criteria for progressive disease not met

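### A relapsed/refractory patient who enters below 5% marrow blasts, without Auer rods or extramedullary disease, can count as a responder in the primary endpoint with no change from baseline

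*Combined protocol and SAP*

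**What the plan says.** **Entry.** Section 12.1.2 asks previously untreated patients for at least 20% blasts in blood or marrow, or for extramedullary involvement. For relapsed/refractory patients it accepts "any abnormal disease burden as detected by morphology, flow cytometry, cytogenetics, or molecular testing", provided the 11q23 lesion is detectable. Criterion 3.1.9 asks for detectable abnormal blasts or extramedullary disease and also sets no blast percentage.

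**Response categories (12.1.4.1).**
- CR and CRi share the core "Bone marrow blasts < 5%; no circulating blasts, no blasts with Auer rods, no extramedullary disease" and differ only in neutrophil and platelet counts.
- MLFS is "Bone marrow blasts < 5%; no blasts with Auer rods, no extramedullary disease; no hematologic recovery required".
- PR is the only response category that refers to pre-treatment blasts.
- Stable disease is "Absence of CR, CRi, MLFS, PR; criteria for progressive disease not met".
- For progression by marrow blasts, "a minimum 15% point increase is required in cases with < 30% blasts at baseline".

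**Assessment and counting.** Section 12.1.3 takes as the marrow measure "The percentage of blasts found on the aspirate differential", read at the enrolling institution. Section 12.1.1 treats patients as evaluable for response if, with measurable disease at baseline, they "have received at least one cycle of therapy, and have had their disease re-evaluated". Section 9.1 counts patients who "achieve a CR, CRi, PR, or morphologic leukemia-free state (MLFS), with or without MRD, at any time point". It continues to stage 2 with at least 4 responders of 19 and declares success with at least 11 of 36. It tests 20% against 40%, with both error rates set at 0.10.

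**The concern.** The entry rule and the response rule overlap. Below 5% marrow blasts is an admissible starting point for a relapsed/refractory patient and is also the marrow criterion for three of the four counted response categories. Because stable disease is available only when those categories are not met, an unchanged low-burden patient cannot be scored stable.

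Response is the only endpoint behind the go/no-go rules. A count that includes patients in whom nothing happened does not measure the combination's activity in the way that the 20% and 40% benchmarks imply. A decision on how to score such patients taken after their marrows are read would be post hoc.

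**Working it through.** **1. Following one patient through the text.** Take a relapsed/refractory patient with 2% abnormal marrow blasts, no Auer rods and no extramedullary disease, at 2% again at the end of cycle 1.
- Entry: meets 3.1.9 (abnormal blasts detectable) and 12.1.2.
- Evaluable: one cycle received, disease re-evaluated.
- Category: MLFS. With no circulating blasts the patient is CR or CRi, depending on blood counts. As written, MLFS has no circulating-blast condition, so circulating blasts block CR and CRi but not MLFS.
- Stable disease: unavailable, because a response category is met.
- Primary endpoint: responder.

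A rise from 1% to 4% still meets the MLFS marrow criterion and is 3 points, short of the 15 required for progression by marrow.

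**2. The plan's own design.** Inputs from 9.1: n1 = 19, n2 = 17, continue at ≥4, success at ≥11.

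P(positive | p) = Σ over x from 4 to 19 of b(19, x, p) × P[Bin(17, p) ≥ 11 − x]

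This gives 0.0861 at p = 0.20 and 0.9024 at p = 0.40. The stated limits of 0.10 and 0.90 are met, and a minimax search returns the same 19/36 design.

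**3. Illustration.** Assumptions that the documents do not supply:
- k low-burden patients among the 36, split between stages at random (hypergeometric);
- each is scored a responder with probability q, the chance of meeting CR, CRi or MLFS on at least one on-treatment marrow;
- all other patients respond at 0.20.

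For k = 1 and q = 1, the probability is 0.1436 if the patient falls in stage 1 and 0.1387 if in stage 2. Weighted: (19/36) × 0.1436 + (17/36) × 0.1387 = 0.1413.

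| q | k = 1 | k = 2 | k = 3 | k = 4 |
|---|---|---|---|---|
| 1.0 | 0.141 | 0.220 | 0.325 | 0.453 |
| 0.7 | 0.121 | 0.164 | 0.218 | 0.281 |
| 0.5 | 0.107 | 0.131 | 0.158 | 0.189 |
| 0.3 | 0.093 | 0.100 | 0.108 | 0.116 |
| 0.2 | 0.086 | 0.086 | 0.086 | 0.086 |
| 0.1 | 0.079 | 0.073 | 0.067 | 0.061 |

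The probability reaches 0.10 at q of about 0.40, 0.30, 0.26 and 0.25 for k = 1 to 4.

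**4. The same patients under the other null.** Hold the overall scored rate at 20% with q = 1. The remaining patients then respond at (36 × 0.20 − k)/(36 − k), which is 6.2/35 = 0.177, 5.2/34 = 0.153, 4.2/33 = 0.127 and 3.2/32 = 0.100. P(positive) is 0.0751, 0.0628, 0.0492 and 0.0345, all below 0.10.

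**The case against.** **The size is unknown.** This stands. The documents do not say how many such patients are expected. Retention is also unknown: section 2.1 describes a disease at high risk of poor response or early relapse, and the first on-treatment marrow may be taken at count recovery rather than near day 28.

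**The test is not broken for the rate it names.** This also stands. Section 9.1 sets the null for the response rate as scored. Step 3 uses a different null, 20% in the other patients only. A reader might infer from the table that the trial's type I error exceeds 0.10; step 4 shows that this does not follow from the documents.

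**The exposed group is narrow.** Agreed. A reader might infer that every relapsed/refractory patient, or every patient with a clear marrow, is an automatic responder. Extramedullary disease or Auer rods block all three categories while they persist. Nor is it settled that disease seen only by cytogenetics or molecular testing can enter, because 3.1.9 is narrower than 12.1.2 on this.

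**Other text might prevent the scoring.** Section 9.1 speaks of patients who achieve a category, 12.1.4.3 mentions confirmation criteria, 12.1.7 provides independent review, and the definitions are attributed to the 2017 ELN guideline. None closes the gap within these documents. No passage turns achieving into a required change, no confirmation criteria are defined for marrow response, and the reviewer is given no different definition. The guideline itself was not available.

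**Some mitigation exists.** Section 9.4 describes response separately for relapsed/refractory patients and compares 11q23 level by FISH with baseline. That helps interpretation but does not protect the 4/19 and 11/36 rules.

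**Conclusion.** The concern holds as a flaw in the endpoint definition and should be fixed. Applied exactly as written, the plan counts an unchanged relapsed/refractory patient as a responder if marrow blasts were below 5% at entry and there are no Auer rods and no extramedullary disease. This follows from the text and needs no assumption about numbers.

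The effect on the decision rule is conditional. With other patients at 20%, one to four such patients move the chance of a positive trial from 0.086 to between 0.14 and 0.45 at full retention, and to between 0.11 and 0.19 at 50%. Nothing changes at 20% retention, and below that the probability falls. The design arithmetic in 9.1 is correct, and its error rate holds for the overall rate as scored. What is in doubt is whether a counted response reflects an effect of treatment.

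**What to change.** Use the amendment that 13.1 already requires before phase II enrolment.

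1. In 9.1 and 12.1.4.1, count CR, CRi or MLFS toward the primary endpoint only if it is a better category than the one met at baseline, in the order CR, CRi, MLFS. State that a move from CRi to CR through blood counts alone does not count. A patient in MLFS at baseline because of circulating blasts can still count by clearing them, and a patient with baseline extramedullary disease is unaffected. PR already refers to baseline. The change concerns counting only, not treatment.
2. Keep these patients in the 19 and the 36 as non-responders unless they improve. This agrees with 9.5.2, which bases conclusions on all eligible patients.
3. Report them separately, using the baseline and on-treatment marrow flow cytometry and FISH already in the study calendar.
4. Reconcile 3.1.9 with 12.1.2 on patients who have only cytogenetic or molecular disease.

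**Cost.** Wording only, with no extra enrolment. The price is power. If none of these patients improves (q = 0) and the others respond at 40%, power falls from 0.902 to 0.880, 0.853, 0.821 or 0.785 with one to four of them, so the stated 0.90 should be qualified. With the others at 20%, the false-positive probability falls to 0.072, 0.060, 0.049 or 0.040.
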